8.2.1 Primary Performance Endpoint

1. The proportion of subjects ("responders") with the lip volume improved by ≥ 1 point versus baseline value at 6 weeks after initial treatment based on the investigator live assessment using the validated Lip Fullness Scale (LFS).

'Responder' is defined having at least ≥ 1 grade improvement as evaluated with the 5 point-validated LFS at a given visit relative to Baseline score (prior to treatment). Individual LFS grades per visit will be calculated separately for the upper and the lower lip.

8.2.2 Secondary Performance Endpoint

1. The percentage of responders, based on the investigator live assessment at 6, 12 and optional 18 months after the initial treatment using the validated LFS.
2. The percentage of responders based on the independent photographic reviewer's assessments before initial treatment and at Week 6, Month 6, 12 and optional Month 18 after initial treatment, based on photographs and using the validated LFS.
3. The percentage of subjects with an improvement relative to baseline photographs, (subjects who have been rated as "very much improved" or "much improved" or "improved"), based on the investigator assessment at Week 6, Month 6, 12 and optional Month 18 after initial treatment using the 5-point GAIS.
4. The percentage of subjects with an improvement relative to baseline photographs (subjects who have been rated as "very much improved" or "much improved" or "improved"), based on subject assessment at Week 6, Month 6, 12 and optional Month 18 after initial treatment, using the 5-point GAIS.
5. The extent of subject's satisfaction with overall outcome of the treatment, at Week 6, Month 6, 12 and optional Month 18 after initial treatment, assessed by the subject using the Face-Q™ Questionnaire "Satisfaction with Outcome".
6. The extent of subject's satisfaction with augmentation of lips, at Week 6, Month 6, 12 and optional Month 18 after initial treatment, assessed by the subject using the Face-Q™ Questionnaire "Satisfaction with Lips".
7. Subject's perception of pain after initial and touch-up treatment with Saypha® FILLER Lidocaine using the 11-point Numeric Pain Rating Scale (NPRS), where 0 is no pain and 10 is the worst pain imaginable.
8. Percentage of subjects demonstrating an aesthetic effect at Week 6, Month 6, 12 and optional Month 18 based on the investigator's life assessment.
9. Injection volume (initial and touch-up) required for an optimal augmentation of the lips with Saypha® FILLER Lidocaine

8.3 Safety endpoints

The safety of the investigational device will be evaluated using the following endpoint:

- Occurrence and frequency of adverse events.

9 General Statistical Considerations

9.1 Descriptive Statistics

The following descriptive statistics will be calculated for continuous data and for ordered categorical data (ordinal data):

Summary statistics are displayed with the following digits:

Description	Characteristic	Number of decimal places
Count	n	0
Count corresponding to the number of subjects for a group	N	0
Mean	Mean	As in source + 1
Standard Deviation	SD	Mean+1
Minimum	Min	As in source
Median	Median	As in source + 1
Maximum	Max	As in source
Quartile 1	Q1	As in source+1
Quartile 3	Q3	As in source+1
Percentage relative to N #	%	1

Number of decimal places can be more than one, if necessary. All table percentages should be rounded to one decimal place if not stated otherwise.

All data will be presented in the subject data listings.

If either table or listing does not include any observation, then the following placeholder will be used: "NO SUBJECTS MET THE CONDITION FOR INCLUSION".

9.2 Analysis Population

Analysis Population	Definition
Safety Analysis Set (SAF)	The Safety Analysis Set (SAF) consists of all subjects who received at least one administration of the investigational medical device (IMD).
Full Analysis Set (FAS)	The Full Analysis Set (FAS) comprises all subjects who received at least one administration of the IMD and who had at least one post-treatment evaluation of the LFS.
Per-Protocol Set (PPS)	The Per-Protocol Set (PPS) includes all subjects of the FAS who have no major protocol deviations which affect the primary endpoint. Subjects with major protocol deviations which affect the primary endpoint will be excluded from the PPS.

	Statistical Analysis Plan	
	Sponsor: CROMA-PHARMA GmbH	
	Study Number: CPH-101-201479	Version: Final 1.0 Date: 07 Jun 2021

For this purpose, protocol deviations that could interfere with the objectives of the study, use of prohibited concomitant medications/procedures or deviation of the inclusion/exclusion criteria etc. will be assessed as ‘minor’ or ‘major’ in collaboration with the sponsor in the Data Review Meeting (DRM). The criteria for this assessment will be defined before analysis in the SAP. Listings will be prepared to assess the eligibility of all subjects during the DRM.

All safety analyses will be based on the SAF. The primary data set for effectiveness analysis will be the FAS and PPS.

Subjects who have been administered wrong IMD which is different from randomized will be analyzed as randomized (Planned) for FAS and will be analyzed under IMD, which was administered at first, for SAF. These subjects will not be included in PPS.

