7.2 Analysed data sets

Safety Analysis Set (SAF)

The Safety Analysis Set (SAF) consists of all subjects who received at least one administration of the investigational medical device (IMD).

Full Analysis Set (FAS)

The Full Analysis Set (FAS) comprises all subjects who received at least one administration of the IMD and who had at least one post-treatment evaluation of the LFS.

Per-Protocol Set (PPS):

The Per-Protocol Set (PPS) includes all subjects of the FAS who have no major protocol deviations.

Subjects with major protocol deviations will be excluded from the PPS. For this purpose, protocol deviations that could interfere with the objectives of the study, use of prohibited concomitant medications/procedures or deviation of the inclusion/exclusion criteria etc. will be assessed as 'minor' or 'major' in collaboration with the sponsor in the Data Review Meeting (DRM). The criteria for this assessment will be defined before analysis in the SAP. Listings will be prepared to assess the eligibility of all subjects during the DRM.

All safety analyses will be based on the SAF. The primary data set for effectiveness analysis will be the FAS and PPS. Certain sensitivity analyses may be also done in the PPS.

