9.4 Protocol Violation/Deviation

Protocol deviations that could interfere with the objectives of the study, use of prohibited concomitant medications/procedures or deviation of the inclusion/exclusion criteria etc. will be assessed as ‘minor’ or ‘major’ in collaboration with the sponsor in the Data Review Meeting (DRM). Subjects with major protocol deviations will be excluded from the PPS and listings will be provided.

Major PD: PDs with a direct influence on data for the primary endpoint and/or indirect influence on primary endpoint such as major GCP deviations.

For major deviations, a further distinction has to be made between:

- Subject *included* in PPS: subject can remain in PPS although having the major PD (e.g. ICF signature date was wrong, but had been corrected in an acceptable manner)
- Subject *excluded* from PPS: subject must be excluded from the PPS due to the major PD.

Minor PD: PDs without a relevant influence on data for the primary endpoint and no major GCP deviation. A minor PD will not exclude a subject from the per protocol set (PPS).

All safety analyses will be based on the SAF. The primary data set for effectiveness analysis will be the FAS and PPS. Certain sensitivity analyses may be also done in the PPS.

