10.6.2 Secondary Performance Endpoint

1. The percentage of responders, based on the investigator live assessment at 6, 12 and optional 18 months after the initial treatment using the validated LFS.

Percentage of responders, based on the investigator live assessment at 6, 12 and optional 18 months after the initial treatment using the validated LFS will be summarized by number and percentage using PPS and FAS population.

2. The percentage of responders based on the independent photographic reviewer’s assessments before initial treatment and at Week 6, Month 6, 12 and optional Month 18 after initial treatment, based on photographs and using the validated LFS.

Percentage of responders based on the independent photographic reviewer’s assessments before initial treatment and at Week 6, Month 6, 12 and optional Month 18 after initial treatment, based on photographs and using the validated LFS will be summarized by number and percentage using PPS and FAS population.

3. The percentage of subjects with an improvement relative to baseline photographs, (subjects who have been rated as “very much improved” or “much improved” or “improved”), based on the investigator assessment at Week 6, Month 6, 12 and optional Month 18 after initial treatment using the 5-point GAIS.

Percentage of subjects with an improvement relative to baseline photographs (subjects who have been rated as “very much improved” or “much improved” or “improved”), based on investigator assessment at Week 6, Month 6, 12 and optional Month 18 will be summarized by number and percentage using PPS and FAS population.

Listings will be provided for GAIS.

4. The percentage of subjects with an improvement relative to baseline photographs (subjects who have been rated as “very much improved” or “much improved” or “improved”), based on subject assessment at Week 6, Month 6, 12 and optional Month 18 after initial treatment, using the 5-point GAIS.

Percentage of subjects with an improvement relative to baseline photographs (subjects who have been rated as “very much improved” or “much improved” or “improved”), based on subject assessment at Week 6, Month 6, 12 and optional Month 18 will be summarized by number and percentage using PP and FAS population.

5. The extent of subject’s satisfaction with overall outcome of the treatment, at Week 6, Month 6, 12 and optional Month 18 after initial treatment, assessed by the subject using the Face-Q™ Questionnaire “Satisfaction with Outcome”.

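### The SAP's per-protocol set is defined by the Week 6 endpoint but is also used for Months 6, 12 and 18, so a lip-area procedure after Week 6 does not remove a subject from the durability results

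*SAP*

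**What the plan says.** - **Exclusion rule.** Protocol 7.2 has no endpoint restriction: "The Per-Protocol Set (PPS) includes all subjects of the FAS who have no major protocol deviations". SAP 9.2 adds one: "Subjects with major protocol deviations which affect the primary endpoint will be excluded from the PPS".
- **Major and minor.** SAP 9.4 defines major deviations as "PDs with a direct influence on data for the primary endpoint and/or indirect influence on primary endpoint such as major GCP deviations". The other class is "Minor PD: PDs without a relevant influence on data for the primary endpoint and no major GCP deviation", and a minor deviation leaves the subject in the PPS.
- **Timing of the primary endpoint.** SAP 8.2.1 measures improvement "versus baseline value at 6 weeks after initial treatment based on the investigator live assessment".
- **Use at later visits.** Under SAP 10.6.2 item 1, the investigator-rated LFS responder results for Months 6, 12 and 18 "will be summarized by number and percentage using PPS and FAS population". Photographic LFS, both GAIS ratings, FACE-Q and aesthetic effect are also reported in the PPS at the later visits.
- **Text that points the other way.** SAP 9.2 and 9.4 both repeat the protocol's sentence that deviations bearing on the study objectives, and prohibited procedures, are rated at the Data Review Meeting. SAP 9.4 also has a sentence excluding subjects with major deviations without any endpoint limit. Protocol 6.3.5 gives additional aesthetic correction during the study as an example of a major deviation.
- **Objective.** Duration of the aesthetic effect is a main objective (Protocol 5.1, SAP 7.1.1).

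**The concern.** A per-protocol analysis of durability should show how long the device effect lasts in subjects who had nothing else done to their lips. A filler injection at Month 8, say, can change the Month 12 LFS grade but cannot change the Week 6 grade. If deviations are judged only by their effect on Week 6, that subject's Month 12 grade counts as a per-protocol result of the study device.

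The FAS keeps the subject too, and neither document has a rule for assessments made after such a procedure. No planned analysis therefore separates these observations from the rest. Agreement between PPS and FAS at the late visits would say nothing about this source of bias, although a reader of the report could take it as reassurance.

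**Working it through.** **1. The plan's own figure.** The only related number is the Week 6 precision (Protocol 7.1, SAP 9.6), at p = 0.90 with half-width 1.96 × √(p(1−p)/n).
- n = 100: 1.96 × √(0.09/100) = 0.0588, stated as 0.059.
- n = 50 (half of 100, from the 1:1 ratio): 1.96 × √(0.09/50) = 0.0832, stated as 0.083.

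Both reproduce. They concern Week 6 and do not depend on how the PPS treats later events.

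**2. Applying the SAP rule to a procedure after Week 6.**
- Does it influence the Week 6 grade? No, because it happens afterwards.
- Is it a major GCP deviation? Not by any criterion the SAP gives.
- It is therefore minor under 9.4 and the subject stays in the PPS.
- The other stated exclusion, wrong device administered (9.2), does not cover it.

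**3. How much follow-up is exposed.** From the visit schedule, (52 − 6)/52 = 88.5% of the time to Month 12 and (76 − 6)/76 = 92.1% of the time to Month 18 lies after Week 6.

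**4. Illustrative size.** The documents give neither a rate of such procedures nor an expected late responder rate, so x and p below are assumptions. Let p be the true device responder rate at a late visit. Let x be the fraction of subjects who have faded to non-response, are retreated, and are then graded responders.
- Kept in the PPS: p + x.
- Dropped from the PPS: p/(1 − x).
- Counted as non-responders: p.

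| p | x | kept | dropped | counted as non-responders |
|---|---|---|---|---|
| 30% | 5% | 35.0% | 31.6% | 30% |
| 30% | 10% | 40.0% | 33.3% | 30% |
| 50% | 5% | 55.0% | 52.6% | 50% |
| 50% | 10% | 60.0% | 55.6% | 50% |

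Dropping reduces the bias but does not remove it, because the dropped subjects are all non-responders: 0.50/0.90 = 55.6%, still 5.6 points high.

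**5. If retreatment is unrelated to response.** Keeping gives p + x(1 − p), dropping gives p, and counting as non-responders gives p(1 − x). At p = 50% and x = 10% these are 55%, 50% and 45%. Counting as non-responders is then too low, so it belongs in a sensitivity analysis and should not be the only result.

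**6. Scale.** With 100 subjects at a late visit (an assumption), the 95% half-width is 1.96 × √(0.25/100) = 9.8 points at p = 50% and 1.96 × √(0.21/100) = 9.0 points at p = 30%. The bias from keeping them is about half of that at x = 5% and about equal to it at x = 10%.

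**The case against.** **The SAP does not clearly require these subjects to be kept.** It repeats the study-objectives sentence, names prohibited procedures, and contains an unrestricted exclusion sentence, so the Data Review Meeting could remove them. This stands in part: the SAP is internally inconsistent, and it would be too strong to infer that it mandates keeping all contaminated data. However, SAP 9.2 says the rating criteria are to be set in the SAP, and the only criteria given are those in 9.4. The unrestricted sentence covers major deviations, and 9.4 makes this one minor.

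**Such subjects may be withdrawn.** Protocol 6.3.5 allows it, missing values are not imputed (Protocol 7.5) and summaries use scheduled visits (SAP 9.5.2). This helps only in part, because withdrawal is optional and assessments made after the procedure but before withdrawal have no rule.

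**PPS and FAS need not agree at late visits.** This stands. A reader might infer that the definition forces agreement. It does not: wrong-device subjects and those with early deviations leave the PPS at every visit. The supported statement is only that agreement is uninformative about events after Week 6.

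**Month 18 attendees are not the subjects with most reason to seek retreatment.** This also stands. Subjects with no visible effect may finish at Month 12 (Protocol 6.4.12), so those seen at Month 18 are selected for a lasting effect.

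**Not every prohibited procedure moves the LFS.** Nothing in the documents shows that toxin, laser or peeling shifts it by a grade. The illustration fits added volume best.

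**A single PPS tied to the primary endpoint is a normal choice, and the late endpoints are descriptive.** That limits the weight of the point. It does not justify using that set unaltered for a main objective measured months later.

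**Conclusion.** The point holds for the per-protocol results at Months 6, 12 and 18. Applied as written, the definitions in SAP 9.2 and 9.4 leave subjects with a lip-area procedure after Week 6 in those results, contrary to Protocol 6.3.5 and to other sentences in the same SAP sections. SAP 11 lists only the interim photographic endpoint as a change. Protocol 7.7 asks for a protocol amendment where a deviation from the planned analysis affects effectiveness.

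The size is unknown. Under the assumed 10% retreated after fading, the inflation is 10 points if they are kept, against 5.6 points (true 50%) or 3.3 points (true 30%) if they are dropped. If no such procedures occur, the bias is zero.

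A reader might go further and doubt the primary result. The documents do not support that: a later procedure cannot alter a Week 6 grade, and the Week 6 analysis is unaffected. Removing such subjects from the PPS altogether would discard valid Week 6 data.

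**What to change.** 1. In SAP 9.2 and 9.4, classify deviations against the endpoint at each visit and make the PPS visit-specific. Effectiveness observations after a lip-area augmentation or other prohibited lip-area procedure leave the PPS. Earlier ones, including Week 6, stay.
2. Align the unrestricted exclusion sentence in 9.4 with this rule.
3. For the LFS responder endpoints, add a sensitivity analysis that counts such subjects as non-responders from the date of the procedure, because exclusion alone still favours the device when retreatment follows fading.
4. List the change in SAP 11 and consider whether Protocol 7.7 calls for an amendment.
5. Reconcile two sets of protocol statements. Section 6.3.4 bars lip-area filler and other procedures until the end of the investigation. Sections 6.3.8, 6.3.9 and 6.4.12 say new injections may be given after about 3 months once no effect remains. Until these agree, it is unclear which procedures count as deviations. Naming lip-area augmentation explicitly in item 1 lets the analysis rule work either way.

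The cost is SAP wording, one date comparison per subject and visit, slightly smaller late-visit PPS numbers and one extra table. Protocol 6.4.3 already has subjects asked at each visit about aesthetic procedures in the treated area, with procedures documented in the eCRF. The fix assumes that their dates are recorded and that procedures elsewhere in the lip area are captured too.

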9.3 Definitions

In the following table, the definitions and calculation of derived variables are summarized

Variable / Term	Definition / Way of calculation
Adverse Event (AE)	Adverse Event (AE) any untoward medical occurrence, unintended disease or injury or untoward clinical sign (including abnormal laboratory findings) in subjects, users or other persons, whether or not related to the IMD (for more detail refer to Clinical Investigation Plan section 14)
Adverse Device Effect (ADE)	Adverse Device Effect (ADE) is an AE related to the use of the IMD (for more detail refer to Clinical Investigation Plan section 14)
Serious Adverse Event (SAE)	Serious Adverse Event (SAE) is an AE that led to serious deterioration in the state of health including possible death (for more detail refer to Clinical Investigation Plan section 14)
Serious Adverse Device Effect (SADE)	Serious Adverse Device Effect (SADE) is an ADE that has resulted in any of the consequences characteristic of an SAE.
Unanticipated Serious Adverse Device Effect (USADE)	Unanticipated Serious Adverse Device Effect (USADE) is defined as a SADE which by its nature, incidence, severity or outcome has not been identified in the current version of the Investigator’s Brochure (IB).
Device deficiency	Device deficiency is any inadequacy of a medical device with respect to its identity, quality, durability, reliability, safety or

	Statistical Analysis Plan	
	Sponsor: CROMA-PHARMA GmbH	
	Study Number: CPH-101-201479	Version: Final 1.0 Date: 07 Jun 2021

Variable / Term	Definition / Way of calculation
	performance. This may include malfunctions, use errors, and inadequate labelling
Device deficiency that might have led to an SAE	Device deficiency that might have led to an SAE if a) suitable action had not been taken, or b) intervention had not been made, or c) if circumstances had been less fortunate, is classified as a special type of deficiency and is handled under the SAE reporting system
Baseline	The last valid value prior to IMD administration
Change from baseline at visit n	The difference between a value at time point n and the value at baseline.
Study duration [days]	The duration of the clinical investigation will be a maximum of eight weeks for each participating subject in Cohort I. Date of last visit or “last day on study or last contact” (whichever is latest) – date of informed consent + 1
Volume (mL)	Volume (mL) administered at the applicable visit
Total Volume (mL)	Sum of volume (mL) of administered IMD in all visits

9.4 Protocol Violation/Deviation

Protocol deviations that could interfere with the objectives of the study, use of prohibited concomitant medications/procedures or deviation of the inclusion/exclusion criteria etc. will be assessed as ‘minor’ or ‘major’ in collaboration with the sponsor in the Data Review Meeting (DRM). Subjects with major protocol deviations will be excluded from the PPS and listings will be provided.

Major PD: PDs with a direct influence on data for the primary endpoint and/or indirect influence on primary endpoint such as major GCP deviations.

For major deviations, a further distinction has to be made between:

- Subject *included* in PPS: subject can remain in PPS although having the major PD (e.g. ICF signature date was wrong, but had been corrected in an acceptable manner)
- Subject *excluded* from PPS: subject must be excluded from the PPS due to the major PD.

Minor PD: PDs without a relevant influence on data for the primary endpoint and no major GCP deviation. A minor PD will not exclude a subject from the per protocol set (PPS).

All safety analyses will be based on the SAF. The primary data set for effectiveness analysis will be the FAS and PPS. Certain sensitivity analyses may be also done in the PPS.

9.5 Data Handling

9.5.1 Imputation of Missing data

Effectiveness: For both FaceQ questionnaires the following rule applies: If missing data is less than 50% of the scale's items, insert the mean of the completed items

FACE-Q type	Scenario	Imputation method
FACE-Q-10 (Satisfaction with Lips)	Up to 4 items missing i.e <=4	Mean of non-missing score will be imputed for those missing <=4 items. *(Mean value will be rounded to nearest integer)
	>4 items missing	No imputation will be done, and missing items will be set to missing.
FACE-Q-6 (Satisfaction with Outcome)	Up to 2 items missing i.e <=2	Mean of non-missing score will be imputed for those missing <=2 items. *(Mean value will be rounded to nearest integer)
	>2 items missing	No imputation will be done, and missing items will be set to missing.

Safety: To handle missing or partial AE and concomitant medication date, the following rules will be applied.

For partial start dates:

1. If the year is unknown, then do not impute the date but assign a missing value.
2. If the month is unknown, then:
 - a. If the year matches the year of the dose date, then impute the month and day of the dose date.
3. If the day is unknown, then:
 - a. If the month and year match the month and year of the first dose date, then impute the day of the dose date.

For partial end dates:

1. If the year is unknown, then do not impute the date but assign a missing value.
2. If the month is unknown, then do not impute the date and mark as ongoing for AE and Concomitant medication.
3. If the day is unknown, then assign the last day of the month.

After implementing the rules above, to determine whether AEs (or medications) with missing start or stop dates are pretreatment or on/after treatment, the following strategy will be used:

1. If the start date and stop date are both missing, then the most conservative approach is taken, and medication is considered to be concomitant medication.

	Statistical Analysis Plan	
	Sponsor: CROMA-PHARMA GmbH	
	Study Number: CPH-101-201479	Version: Final 1.0 Date: 07 Jun 2021

2. If the start date is missing but the stop date is not missing and is on or after the day of study dose administration, then the most conservative approach is taken, and the medication is considered to be concomitant medication.

3. If the start date is missing but the stop date is not missing and is before the day of first study dose and after the date of signed informed consent, then the AE is considered Medical History and medication is considered to be prior medication.

4. If the start date is not missing but the stop date is missing, then the most conservative approach is taken and medication is considered to be concomitant while the AE is defined by start date.

If the Adverse Event Relationship flag is missing, the relationship for adverse event will be imputed and will be considered as related. If the Adverse Event intensity flag is missing, the intensity will be imputed and the maximum intensity will be considered as severity.

